Study sites: Antenatal and postnatal clinics at Mulago Hospital and MU-JHU Research Clinic.

Noting Mulago Hospital is undergoing extensive renovation which may affect client volumes; one or more of KCCA Clinics including Kisenyi Health Center IV, Kawempe Health Centre IV, Komamboga Health Center III, Kawaala Health Center III and Kiswa Health Centre IV and/or China-Uganda Friendship Hospital Naguru and Nsambya Hospital would be added as recruitment sites if inadequate recruitment rates are achieved at Mulago Hospital alone.

Study outcomes

A. Quantitative data outcomes:

[figure not shown]
Primary:

- i) Incidence of one or more STIs during study follow-up, with STIs confirmed by laboratory tests of HIV-1, Neisseria Gonorrhoea, Treponema pallidum (Syphilis), Chlamydia trachomatis, Bacterial Vaginosis or Trichomonas vaginalis.
- ii) Reported (and validated) consistent condom use and uptake of effective contraceptive method
- iii) Acceptability and desirability of assigned clinic service model

B. Qualitative Data Outcomes:

- i) Teen mothers' knowledge, attitudes and practice regarding teen reproductive health and related health services and risk perception and motivation to utilize reproductive health services and use of dual protection methods derived from FGD and single and serial IDIs
- ii) Health providers' knowledge, attitudes and practice regarding provision of adolescent reproductive health services

STUDY SCHEMA

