3.4.5 Randomization procedures

Prior to the study commencing, a randomization list will be prepared by the Data Manager at MU-JHU. This list will be computer-generated using random-sized block groups and will include consecutive intervention numbers with corresponding random intervention assignments. The randomization list will be encrypted in a password-protected file and backed up on the MU-JHU server. Encrypted copies of the original randomization list and documentation of the procedure used to generate the lists will be stored in the project administrative computers in MU-JHU and backed up on the MUJHU server. At enrolment, the MU-JHU Data Center will issue randomization numbers to the study coordinator based on the participants' group allocation. These random numbers will be placed in envelopes and placed at a centralized location where study counselors may access them. After signing the informed consent and the participant is deemed eligible (based on the study eligibility criteria listed above), the participant will then open the sealed envelope and reveal the study group they are randomly assigned to. Assignment of randomization is considered the effective act of participant enrolment.

3.4.6 Intervention (Enhanced Peer Support Education and Counseling):

Routine care is the care currently provided at the hospitals/ health centers during pregnancy, delivery and postpartum.

Per the Uganda clinical guidelines 2012 [33], the main objectives of antenatal care are: prevention and treatment of any complications, emergency preparedness, birth planning, satisfying any unmet nutritional, social, emotional, and physical needs of the pregnant woman, provision of patient education, including successful care and nutrition of the newborn, Identification of high-risk pregnancy and encouragement of (male) partner involvement in antenatal care.

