Routine care in ANC/PNC clinics varies within hospitals/health centers depending on available resources and also among healthcare providers; hence the standard of care described above is not what is provided. The basic minimum that is usually provided is obstetric care, delivery plans and health education which is not standardized and there may be stock-outs of essential laboratory commodities and pharmacy hours are restricted. In practice even at the national referral hospital it is not uncommon for pregnant women not to receive Hemoglobin, syphilis or urine screening tests (as confirmed by triangulated data from women's self-reports in AIS 2011. [6])

The routine care group (control Arm 1) will have their visits conducted in the ANC/PNC clinic following the usual care as provided in these clinics, as summarized above.

The intervention groups will also have the routine care as provided within Mulago hospital or the designated health facility and in addition will have the enhanced interventions which will focus on providing support and education including reproductive health information to the pregnant and postnatal adolescents on their risk of HIV/STI acquisition, and condom use utilizing adolescent friendly IEC materials and interactive exchanges either in a group or one-

to-one. They will also receive counseling on the importance of family planning and those interested will be referred to the family planning clinic for provision of their choice of the effective available family planning methods. In addition, the interventions will also provide education on the importance of delivery in a hospital, post-natal care, infant feeding and importance of immunization for the baby. Both enhanced intervention groups will receive pre appointment reminders of follow up appointments through sms or phone calls if they agree. The adolescent group education counseling sessions will be done by trained, experienced peer educators during around 6 sessions conducted in the MU-JHU clinic. The one-to-one peer support and education counseling sessions will occur in the ANC for pregnant adolescents (in different clinic space from the routine care group) and postpartum the sessions will be held in the adolescent clinic (ward 15) in Mulago Hospital. The enhanced intervention sessions will occur in different places from each other and from the control group so as to minimize cross-contamination between the groups.

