3.7 Statistical considerations and analysis plan

3.7.1 Sample size determination

Sample size determination

Sample size for this study was based on the outcomes, uptake of effective contraceptive, or prevalence of STIs, at last follow-up comparing each of the two interventions to the control in this three-arm trial. We assumed the uptake of effective contraceptives and consistent condom use as a composite outcome to be 10% [38] (in control/standard), 30% and 35% at the last follow-up in the two intervention arms. At 80% power, and 5% type 1 error rate, and a 10% loss to follow-up, the sample size in the intervention arms was 100 (each 50), while the control/standard was adjusted to 71; this follows a recommendation by Fleiss et al for multiple-arm trials that control arms have a bigger sample size than the intervention.

For the prevalence of STIs, we assumed 20%[10] in control/standard arm, 10% in the intervention-1, and 8% in intervention-2 at the last follow-up, suggesting an average of 55% reduction in prevalence of STI. With similar power of 80%, 5% type-1 error rate and 10% loss to follow-up, a total of 215 respondents in control/standard arm, and 152 per each of the intervention arms resulting in a total of 519. Since 519 respondents are sufficient to address the objectives of the uptake of effective contraceptives + consistent condom use, we determined that the final sample size for this study will be 519 (215 control/standard arm; 152 per each of the two intervention arms).

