3.7.2 Statistical analysis

Exploratory data analysis will be conducted on all variables including the binary outcomes. Descriptive statistics will be generated providing proportions (percentages) for categorical data, and mean (SD)-for normally distributed data, and median (IQR) nonnormal continuous variables. A consort diagram will also be generated to show the time of enrollment, and follow-up. Bar charts showing the distribution of categorical data will also be generated. Data will be assessed for missingness especially as a result of non-follow-up in this prospective study design. In order to address this concern, a comparison of non-follow-up and those followed up will be done, and propensity scores will be constructed to use as weights in the regression models. For categorical/dichotomous outcomes, we will use Fishers Exact Test or chi-square as appropriate, and will report the respective 95% confidence intervals around point estimates, which offer important interpretation for the trial findings.

Primary outcome-1: Composite measure of consistent condom-use and use of an effective FP method. A comparison of this binary outcome will be conducted at the last follow-up. A log-

binomial regression model will be used to obtain the prevalence rate ratios (PRR) as the measure of effect or association, because the outcomes are greater than 10%. The primary exposure variable is study arm. The two intervention arms will be compared to the control arm in the same model. Potential confounders will be adjusted for, after assessing for interaction of some variables with the study-arm in the association with the primary composite outcome. Respondents from the same facility may be correlated, and so adjustment for potential clustering of observations within the selected facilities will be done.

Primary outcome-2: Incidence of any STI. Kaplan-Meier survival analysis will be conducted to determine differences in the probability of STI infection between study arms. Differences in the KM will be determined by log-rank test. Further analysis will be conducted using Poisson regression models to obtain incidence rate ratios (IRR) comparing the two intervention arms to the control arm in the same model. Potential confounders will be adjusted for, after assessing for interaction of some variables with the study-arms in the association with the incidence of STI. Adjustment for potential clustering of observations within the selected facilities will be done.

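### Section 3.7.2 adjusts both regression models for clustering by recruiting facility without naming a method; a facility-clustered variance, one ordinary way to do it, is unreliable with the two to eight facilities named and impossible with one

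*Combined protocol and SAP*

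**What the plan says.** Section 1.1 states that participants are individually randomised to the three arms. Section 3.4.5 describes one blocked list and mentions no stratification by facility: "This list will be computer-generated using random-sized block groups and will include consecutive intervention numbers with corresponding random intervention assignments".

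Recruitment is planned from Mulago Hospital. The Protocol Summary names five KCCA clinics and two further hospitals, one or more of which "would be added as recruitment sites if inadequate recruitment rates are achieved at Mulago Hospital alone".

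Section 3.7.2 plans a log-binomial model for the composite of consistent condom use and effective contraception, with both intervention arms compared to control in the same model. It then says: "Respondents from the same facility may be correlated, and so adjustment for potential clustering of observations within the selected facilities will be done". For STI incidence it lists Kaplan-Meier curves and a log-rank test first, with no clustering adjustment described. A Poisson model for incidence rate ratios follows as further analysis, and the facility adjustment is repeated there. The section names Stata 12 but does not say how the adjustment will be made or what happens if only Mulago recruits.

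**The concern.** Adjustment for clustering is needed when the clusters are what is randomised, or when treatment is delivered in clusters. Neither is true of the recruiting facility here. Women in all three arms attend the same facilities, so a facility effect is shared across arms and largely cancels in the arm contrast. What remains is chance imbalance of facilities between arms, which a woman-level variance already reflects.

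The reason the plan gives, that respondents at one facility may be correlated, is the usual reason for correcting a variance. A common correction computes the standard error from the scatter of facility totals and refers the result to the normal distribution. That is justified only with many clusters. With a handful, the standard error is itself very poorly estimated and the normal critical value is too small.

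At stake are the interval and p-value for the composite outcome, and those for the STI incidence rate ratio.

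**Working it through.** **Benchmark.** Section 3.7.1 sets the error rate and loss: "With similar power of 80%, 5% type-1 error rate and 10% loss to follow-up". It does not state sidedness; two-sided is assumed. The STI sample size can be matched by taking 20% against 9%, the mean of the two intervention rates, with a pooled two-sided formula, allocation 1 : 1/√2 and division by 0.90. That gives 219 control and 155 per intervention arm, against the stated 215 and 152, within 3%. The stated inputs include no design effect for facility. This match only fixes the setting; nothing below depends on it.

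**Inputs.**
- Analysed numbers after 10% loss: 215 × 0.90 ≈ 193 control; 152 × 0.90 ≈ 137 per intervention arm.
- Event rates: 20% (STI, control) and 10% (composite, control), both from 3.7.1.
- Facilities G: one planned (Mulago); named in all, 1 + 5 + 2 = 8. Sections 3.2.1 and 3.4.1 each omit one of the clinics, so those lists give 7.
- Assumed, because the documents give no figure: facility intraclass correlation of 0 or 0.02, and facility shares.

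**Analytic check.** For a clustered variance with the G/(G−1) factor and roughly equal facilities, the test statistic behaves like t with G−1 degrees of freedom. Referring it to 1.96 gives a false-positive rate of P(|t with G−1 df| > 1.96). For G = 2 this is 1 − (2/π)·arctan(1.96) = 30.0%.

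**Simulation under no effect.** Women were randomised individually, at 3,000 to 6,000 trials per setting. Models were a log-link arm model and a Poisson model with age and education. The "equal sizes" column below spans all settings run, or shows the single Poisson setting. The 60% and 80% columns are from the Poisson model at a 20% event rate and correlation 0.02. Follow-up time was not varied.

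| Facilities | Analytic | Equal sizes | One site 60% | One site 80% |
|---|---|---|---|---|
| 1 | not computable | – | – | – |
| 2 | 30.0% | 29-31% | 31% | 36% |
| 3 | 18.9% | 19-20% | 21% | 31% |
| 4 | 14.5% | 14-15% | 19% | 30% |
| 6 | 10.7% | 10% | 17% | 29% |
| 8 | 9.1% | 8-9% | 16% | 26% |

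Without the G/(G−1) factor the equal-size rates are 40% at two facilities and 10.5% at eight.

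**Alternatives in the same settings.**
- Woman-level robust standard errors, no facility term: about 4-6%.
- Facility fixed effects with woman-level robust standard errors: about 4-6%.
- Facility-clustered standard errors with t(G−1) critical values: 4-5.5% with equal facilities, but 5-10% with one site at 60%. The critical values are 12.7 at G = 2 and 4.3 at G = 3, which would cost most of the power.

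**What the woman-level variance does not cover.** Arm 2 is delivered in groups of 8-12 (Table 2). Take groups of 10 and an assumed within-group correlation of 0.02 to 0.05. The design effect in Arm 2 is 1 + 9 × 0.02 = 1.18 to 1 + 9 × 0.05 = 1.45. The variance of the Arm 2 contrast then rises by (1.18/137 + 1/193) ÷ (1/137 + 1/193) ≈ 1.11, up to 1.26 with 1.45. Referring 1.96/√1.11 and 1.96/√1.26 to the normal gives roughly 6% to 8%. This is a separate source of correlation.

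**The case against.** The strongest reply is that 3.7.2 names no method. A facility fixed effect, a random intercept, GEE or a clustered standard error would each count as adjustment for clustering, and the fixed effect holds about 5%. That stands. A reader might infer that the plan commits itself to an inflated error rate; the documents do not support this. The rates in the table describe one possible implementation.

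Four further limits also stand.
- The rates do not apply to the one-facility base plan. There the adjustment simply cannot be carried out.
- A reader might extend the point to every primary test. The log-rank test, listed first for STI, carries no clustering adjustment, so it is outside this point.
- A reader might take section 3.4.6 as evidence that outcomes differ by facility. It says: "Routine care in ANC/PNC clinics varies within hospitals/health centers depending on available resources and also among healthcare providers". That describes variation within facilities and between providers, and no outcome by facility is reported anywhere.
- Eight is the number of facilities named, not a ceiling, because the clinic lists are introduced as examples. Nor does 3.7.2 exclude facility as a covariate, since age and education are given only as examples of confounders.

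What the reply does not remove is the choice itself. The wording points towards a variance correction. Leaving the method open allows a choice, possibly after the data are seen, between options whose error rates run from about 5% to 30% or more.

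**Conclusion.** The concern holds in conditional form. The plan adjusts two models for a clustering that individual randomisation does not require, leaves the method unnamed, and has few facilities to work with. If the adjustment is a facility-clustered variance with normal critical values, the false-positive rate per comparison is about 30% with two facilities, 14-15% with four and 8-9% with eight equal ones. With eight facilities and one site holding 60% or 80% of the women it is 16% or 26%. With one facility there is no estimate at all.

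This concerns the log-binomial analysis of the composite and the Poisson rate ratio for STI. It rests on the assumed method, on two-sided testing, and on assumed facility shares and correlation. A dominant Mulago is plausible because the other sites are back-ups, but the documents give no shares.

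The absence of stratification by facility in 3.4.5 might look like a flaw of equal weight. It is not: woman-level analysis held about 4-6% without it.

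**What to change.** In 3.7.2, replace both clustering sentences with:

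> Recruiting facility enters both models as a fixed effect (small facilities combined; the term is dropped if only one facility recruits), with standard errors robust at the level of the woman and not clustered on facility.

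State the rule for combining small facilities before outcome data are seen. Add that this wording does not preclude separate handling of correlation within Arm 2 peer groups.

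Optionally, if enrolment has not started, prepare a separate blocked list for each facility in 3.4.5. This improves balance but is not needed for validity, and it means more envelope sets to manage.

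The main cost is SAP wording. The statistical cost is up to about seven extra parameters if all eight named facilities recruit. At the assumed 10% control rate there are only about 19 expected control events (0.10 × 193), so the log-binomial model may struggle to converge. The SAP should name a fallback in advance, for example the log-link Poisson model with the same fixed effects and woman-level robust standard errors, which held about 4-6% in the check above.

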We will conduct a 3-arm, randomized, controlled trial of 519 pregnant adolescents aged 15 through 19 years at enrollment to test the acceptability and effectiveness of two enhanced adolescent friendly reproductive health prevention interventions versus current routine care. In each intervention group, 152 adolescent mothers will be randomized to either the enhanced group peer support education and counseling intervention or to the enhanced one-to-one (individual) peer support education and counseling group with a young, model, peer educator trained to deliver RH education and counseling messages, beginning during pregnancy (≥ 28 weeks) and followed up to 9 months postpartum or study end at or after 6 months (whichever comes first). The control group will consist of 215 adolescent mothers randomized to routine care as provided at Mulago hospital (or the designated health facility) where midwives deliver group sessions during antenatal and postpartum care visits as well as standard PMTCT services including routine opt-out HIV C&T and availability of partner C&T. Syphilis testing should also be routinely provided and treatment provided for infected pregnant mothers and their partners as per local standard of care.

The 3 groups will be enrolled with study visits at 3, 6 and 9 months post-partum however the intervention groups (Arms 2 and 3) will have additional visits at 36 weeks Antepartum, delivery, 6 and 10 weeks postpartum, Quantitative baseline data will be collected on routine demographic characteristics, reproductive history, pregnancy intentions and sexual risk/perceptions and HIV/STI status.

Summarized table 1 of the study schedule and evaluation

	SCR/ ENR	36 weeks APT	Birth†	6 weeks PPT	10 weeks PPT	3 months PPT	6 months PPT	9 months PPT†
Arm 1– Routine Care	X					X		X
Intervention: Enhanced Counseling Education Sessions/Routine care as provided	X			X	X	X	X	X
Behavioral Assessments using IAQ and ACASI	X				X		X	X
Psychosocial Assessment	X					X		X
Obtain/review and update RH and Medical History	X	X	*	*	*	*	*	X
Clinical Examination – Blood Pressure, Weight, Obstetric exam	X	X						
Prescribe contraceptives				X	*	*	*	*
Provide available test results	X	X		*	*	X	*	X
Provide treatment/referral as appropriate	*	*	*	*	*	*	*	*
LABORATORY								
Blood	HIV-1 Serology (rapid tests)	X					X	X
	Syphilis serology RPR (TPAB if positive)	X				€		X
Urine	Protein and Glucose	X	X					
	Rapid test for Gonorrhoea infection	X	*		*	*	*	X

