	Rapid test for Chlamydia infection	X	*		*	*	*	X
	HCG test				*	*	*	X
Pelvic	Rapid test for Trichomoniasis	X	*		*	*	*	X
	Collect Vaginal swab for Bacterial Vaginosis testing	x	*		*	*	*	X
	Collect vaginal swab for testing presence of Y chromosome ‡							X
QUALITATIVE COMPONENT								
Serial In-depth Interview (SIDI)	X				X			X
Focus Group Discussion (FGD)	X							X
Single In-depth Interview (IDI)				*	*	*	*	*

X mandatory, *If indicated, †contact at birth only for the intervention groups, € repeat at 6months if positive at enrolment, ‡ done only at study exit for participants with self-reported consistent condom use,

† month 9 will be the study exit visit for most participants however month 6 may the exit visit for the last participants to enroll hence additional exit evaluations would be done then

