
*Only at 3 months and study exit (month 9 or 6 for the last participants to enroll), † Pre/posttest counseling and HIV testing done only at 3 months and study exit, ‡ STI lab tests done at study exit and when clinically indicated, ¥done at 36 weeks of gestation for all study groups, ‡ done only at study exit for participants with self-reported consistent condom use

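### STI incidence is compared between arms with unequal chances of detection: four of the six infections have a mandatory post-baseline test only at exit, and Arms 2 and 3 have more earlier visits where an if-indicated test can occur

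*Combined protocol and SAP*

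**What the plan says.** **Analysis.** For incidence of any STI, Section 3.7.2 plans that "Kaplan-Meier survival analysis will be conducted to determine differences in the probability of STI infection between study arms" and that "Differences in the KM will be determined by log-rank test". Poisson models then give incidence rate ratios for each intervention arm against control.

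**Tests.** In Table 1 (Section 3.1) and Appendix B, gonorrhoea, chlamydia, trichomonas and bacterial vaginosis are marked X at enrolment and in the last column, with asterisks between. The key reads "X mandatory, *If indicated". Some table cells are broken in the text available, but a footnote to Table 3 (Section 3.5.1.1) says the same in words: "STI lab tests done at study exit and when clinically indicated". Exit is normally month 9, but "month 6 may the exit visit for the last participants to enroll hence additional exit evaluations would be done then". HIV differs: its tests are at 3 months and exit in all arms.

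**Visits.** Section 3.1 says "The 3 groups will be enrolled with study visits at 3, 6 and 9 months post-partum", but the "intervention groups (Arms 2 and 3) will have additional visits at 36 weeks Antepartum, delivery, 6 and 10 weeks postpartum". The Arm 1 row of Table 1 marks only 3 and 9 months after enrolment. Table 2 (Section 3.5) puts the control arm's next study visit at 3 months postpartum. A Table 3 footnote has urine protein and glucose "done at 36 weeks of gestation for all study groups".

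**Treatment.** Under Section 3.5, curable STIs found during follow-up are treated.

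Section 3.7.2 has no rule for unequal testing opportunity and no planned tabulation of interim tests by arm.

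**The concern.** An infection that starts and clears between enrolment and exit is counted only if someone tests for it in that window. Arms 2 and 3 have more scheduled occasions for that, so with identical true incidence they can record more events, and record them earlier. Randomisation does not remove this, because the difference arises after assignment. The planned adjustment for age and education and the weights for loss to follow-up do not address it either.

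The trial hypothesises superiority (Section 1.2.1), and Section 6.2 ties scale-up to reduced HIV/STI incidence. A detection artefact could dilute a real benefit or make peer support look harmful.

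**Working it through.** **Sizing figure.** Section 3.7.1 assumes STI prevalence at last follow-up of 20% in control against 10% and 8%. For 20% vs 10%, 80% power, one-sided 5%, pooled variance and allocation 152/215, the two-proportion formula gives 192 and 136. Dividing by 0.9 gives 214 and 152, against the stated 215 and 152 (215 + 2 × 152 = 519). The point does not depend on this, but the sizing quantity is a proportion at the last visit, not a time to event. With 10% loss, 215 × 0.9 ≈ 194 and 152 × 0.9 ≈ 137.

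**Visits with an if-indicated test.** Reading the broken rows as 36 weeks, 10 weeks, 3 months and 6 months, the intervention-only visits number:
- 2 of 4 under the Section 3.1 text (36 weeks, 10 weeks);
- 3 of 4 under the Table 1 Arm 1 row (also 6 months);
- 1 or 2 respectively, if the 36-week footnote means controls attend then.

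**Illustrative model.** The documents give no infection duration or interim testing rate, so the following are assumptions: enrolment at 30 weeks' gestation; interim visits at study weeks 6, 20, 24 and 36; exit at week 49; true cumulative risk 20% in every arm; mean duration D of 13, 26 or 52 weeks, or infinite; probability q of 0.2, 0.4 or 0.6 that an infected attendee is tested at an interim visit.

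- Hazard λ = −ln(0.80)/49 = 0.00455 per week.
- Per half-week: a = 1 − exp(−λ/2) = 0.00227; b = 1 − exp(−0.5/D).
- Uninfected: U′ = U(1 − a) + I·b. Infected: I′ = I(1 − b) + U·a.
- At an interim visit qI is detected; at exit all of I is detected.
- Null rate ratio = (detected ÷ person-weeks in Arms 2/3) ÷ (the same in control).
- For the exit-only count, detected infections are cured and return to U.

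**One setting in full (D = 26, q = 0.4).**
- Arms 2/3: 0.00972 + 0.02234 + 0.01782 + 0.02275 + 0.06192 = 0.13455 over 47.19 person-weeks.
- Control at 3 and 6 months: 0.02750 + 0.02660 + 0.06606 = 0.12016 over 47.97.
- Rate ratio = (0.13455/47.19) ÷ (0.12016/47.97) = 1.14.
- Any-detection risk ratio = 0.13455/0.12016 = 1.12.
- Exit-only ratio = 0.0661/0.0689 = 0.96.

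**All finite-duration settings, no true effect:**

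| Control's interim visits | Rate ratio | Any-detection ratio | Exit-only ratio |
|---|---|---|---|
| 3 and 6 months | 1.06–1.24 | 1.05–1.22 | 0.93–0.99 |
| 3 months | 1.09–1.49 | 1.08–1.46 | 0.66–0.93 |
| 36 weeks, 3 and 6 months | 1.04–1.11 | 1.03–1.11 | 0.95–0.99 |
| 36 weeks and 3 months | 1.07–1.31 | 1.06–1.29 | 0.67–0.93 |

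With q = 0 every ratio is 1.00. If infections persist until treated, the rate ratio is 1.01–1.03, because only person-time differs, and the any-detection ratio is exactly 1.00. The exit-only ratio is then 0.89–0.92 (control at 3 and 6 months) or 0.58–0.80 (3 months only).

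**Consequence.** In 20,000 simulated trials per setting (194 vs 137, no true effect), log-rank shows false harm in about 4–10%, 6–23%, 4–6% and 5–14% for the four rows, against a nominal 2.5%. If true risks are 20% and 10% (hazard ratio ln 0.90/ln 0.80 = 0.47), the recorded rate ratio is 0.52–0.60 or 0.54–0.72 for the first two rows.

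**Sensitivity of the null rate ratio (first two rows unless stated).**
- q of 0.05–0.10: 1.02–1.09 and 1.03–1.15.
- Controls tested at half the rate at the intervention-only times: 1.03–1.11 and 1.04–1.19.
- No new infections for 6 weeks after birth: 1.05–1.21 and 1.09–1.47.
- Half of participants exiting at 6 months: 1.03–1.41 over all four rows.
- 20% prevalence at exit instead of 20% cumulative risk: 1.04–1.57 over all four rows.

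**The case against.** **The method is not the cause.** This stands. A reader might infer that log-rank and Poisson should give way to a binary outcome of any STI detected by exit. The figures do not support that: the null ratio moves only from 1.06–1.24 to 1.05–1.22, or from 1.09–1.49 to 1.08–1.46. The binary form stops treating visit dates as infection times, but it keeps nearly all the bias when infections clear.

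**The size is assumed.** This also stands. Section 1.1 says symptoms predict STIs poorly in women, so few infected attendees may trigger a test, and rarer testing shrinks the ratio. Section 3.4.6 lists routine postpartum contacts at 6 and 10 weeks and later, where controls might be tested. The same section says routine screening tests are often not done, so it is unclear how far those contacts close the gap. HIV, part of the composite, is tested alike in all arms, and the single-infection model leaves it out.

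**The bias is conservative.** True only for false benefit. Lost effect and apparent harm remain.

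**Exit-only is scheduled alike in all arms and matches the sizing quantity, so it could be the sole primary.** It would depart from the incidence endpoint of Section 3.6.1 and Objective 2.2. It also leans the other way, because infections found and treated earlier leave the count.

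**Conclusion.** The concern holds as a gap in Section 3.7.2: detection opportunity for four of the six infections differs by arm, and nothing planned measures or addresses it. This follows from the test schedule and the visit text, whichever reading of the control visits applies. The direction is against the interventions if interim testing per visit is similar across arms.

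The size is not known. It is nil without interim tests and 1.01–1.03 on the null rate ratio if infections persist until treated. Under the assumed durations and testing rates it is about 1.04–1.49, depending on which visits controls attend, and smaller with rarer testing or with control testing at routine contacts.

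Two stronger readings are not supported. The documents do not show that the planned analysis would produce a false benefit; the bias points the other way. Nor do they show that the result will be materially wrong, since they give no rate of if-indicated testing. The gap should be fixed because the remedy is cheap and readers otherwise could not tell which case applies.

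**What to change.** In Section 3.7.2 keep the planned incidence analysis and add the following.

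1. Pre-specify beside it a comparison of the mandatory exit test by arm. Use the log-binomial model already planned for the other primary outcome, with exit at 6 or 9 months as a covariate and the planned weights for missing exit tests. This is also closer to the quantity used for sizing in Section 3.7.1.
2. Tabulate interim STI tests, positives and treated infections by arm.
3. State that the incidence analysis leans towards more STIs in Arms 2 and 3 and the exit-only analysis towards fewer. A benefit should therefore not be claimed from exit-only alone, and an apparent harm in the incidence analysis should be read against the exit-only result.
4. Reconcile the Section 3.1 text, the Table 1 Arm 1 row, the Table 2 statement on the control arm's next visit and the 36-week footnote to Table 3.

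A binary any-detection analysis may be added, but it need not replace the primary.

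The cost is one more analysis, one table and some text, with no extra tests or visits. Discordant results will need cautious wording.
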